8.2 Populations for Analyses

- The safety population for safety endpoints includes all subjects who receive at least one dose of study medication
- The population for efficacy analysis includes all randomized subjects
- The analysis population for PK assessments will include subjects who have received at least one dose of apixaban and have a PK sample collected
- The analysis population for PD assessments will include subjects who have received at least one dose of apixaban and have a PD sample collected

Pre-specified, descriptive subgroup analysis will be performed for subjects with or without a previous history of thromboembolic events, for subjects with or without aspirin use, and other important subgroups, if applicable. Details will be provided in the Statistical Analysis Plan (SAP).

8.3 Endpoints

8.3.1 Primary Endpoint(s)

Primary efficacy endpoint: This is a safety and PK study, and there is no primary efficacy endpoint in this study.

Primary safety endpoint: A composite of adjudicated major or CRNM bleeding events per the Perinatal and Paediatric Haemostasis Subcommittee of the International Society on Thrombosis and Haemostasis (ISTH) criteria.

Note: bleeding occurring within 24 hours after cardiac catheterization and bleeding occurring within 48 hours after surgery will be analyzed separately. Details will be described in the Statistical Analysis Plan (SAP).

Bleeding definitions are described as follows:

Major bleeding is defined as bleeding which satisfies one or more of the following criteria: (i) fatal bleeding; (ii) clinically overt bleeding associated with a decrease in hemoglobin of at least 20 g/L (i.e. 2 g/dL) in a 24-hour period; (iii) bleeding that is retroperitoneal, pulmonary, intracranial, or otherwise involves the central nervous system; and/or (iv) bleeding that requires surgical intervention in an operating suite, including interventional radiology.

CRNM bleeding is defined as bleeding which satisfies one or both of the following criteria: i) overt bleeding for which blood product is administered and that is not directly attributable to the subject's underlying medical condition; and/or ii) bleeding that requires medical or surgical intervention to restore hemostasis, other than in an operating suite.

Both major and CRNM bleeding events will be adjudicated by a blinded, independent EAC.

8.3.2 Secondary Endpoint(s)

Pharmacokinetics:

Apixaban PK will be characterized using a population PK approach. Nonlinear mixed effects modeling will be used to estimate population and individual PK parameters (e.g., CL/F, Vc/F, Ka), and to explore relationships between these parameters and subject demographics (e.g., age, body weight, gender) as well as estimate Cmax, Cmin, and AUC (TAU) in each subject. Data from this study may be combined with data from prior apixaban pediatric trials.

Chromogenic FX assay (apparent FX level) will be measured to assess apixaban PD. Anti-FXa activity will also be assessed.

Apixaban exposure-response (E-R) relationships may also be explored.

Efficacy:

[figure not shown]
- Any thromboembolic events (intra-cardiac, shunt, inside Fontan pathway, PE, stroke, other arterial or venous thromboembolic events, etc.) detected by imaging or clinical diagnosis, and thromboembolic event-related death

Note: thrombosis occurring within 24 hours after cardiac catheterization and thrombosis occurring within 48 hours after surgery will be analyzed separately. Details will be described in the SAP.

- Death and thromboembolic events will be adjudicated by a blinded, independent EAC
- Patient/proxy reported outcome or quality of life (e.g., pediatric quality of life inventory (PedsQL) generic core and cardiac modules, and Kids Informed Decrease Complications Learning on Thrombosis [KIDCLOT©])

Safety:

- Adjudicated major bleeding
- Adjudicated CRNM bleeding
- All bleeding
- Drug discontinuation due to adverse effects, intolerability, or bleeding
- All cause death

8.4 Analyses

8.4.1 Demographics and Baseline Characteristics

Frequency distribution and summary statistics for demographic and baseline variables will be presented by treatment group (apixaban and active comparator) and for all subjects combined. Key demographic and baseline variables to be summarized include: geographic region, age, gender, race, height, weight, body mass index, vital signs (systolic blood pressure, diastolic blood pressure, respiratory rate and heart rate) and medical history.

8.4.2 Efficacy Analyses

There is no primary efficacy endpoint for this study. For the secondary and other efficacy endpoints, descriptive statistics including event rates will be provided. Difference of event rates and 95% confidence interval (CI) if applicable will also be provided, and relative risk and 95% CI for relative risk will be calculated based on the stratified Mantel-Haenszel's method if applicable. Efficacy analyses will be based on intention to treat (ITT) population.

8.4.3 Safety Analyses

The term “treatment period” refers to the period between the first administration of study drug and two days after the last administration of study drug. This period will be the basis for the summaries of safety.

Primary Safety Analyses

[figure not shown]
For the primary safety endpoints, descriptive statistics including event rates, difference of event rates and 95% confidence interval (CI) will be provided, and relative risk and 95% CI for relative risk will be calculated based on the stratified Mantel-Haenszel’s method if applicable.

Secondary Safety Analyses

The incidence of minor bleeding events and all bleeding AEs occurring through the end of the treatment period will be summarized by treatment group. The incidence of AEs and of marked abnormalities in clinical laboratory tests will be summarized by treatment group. All AEs that are serious or that result in discontinuation of study drug will be described in depth. Changes from baseline in laboratory parameters will be summarized at each measurement time point by treatment group.

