3.5 Discontinuation of Subjects from Treatment

Subjects MUST discontinue the investigational product (and non-investigational product at the discretion of the investigator) for any of the following reasons:

- Subject's request to stop study treatment
- Any clinical AE, laboratory abnormality or intercurrent illness which, in the opinion of the investigator, indicates that continued participation in the study is not in the best interest of the subject
- Termination of the study by BMS
- Loss of ability to freely provide consent through imprisonment or involuntarily incarceration for treatment of either a psychiatric or physical (e.g., infectious disease) illness
- Use of aggressive life-saving therapies such as LVAD, or ECMO during study
- Receipt of a heart transplantation
- If a subject becomes ineligible for the study drug during the study, (e.g., receives a VAD, ECMO, or a heart transplantation), study drug must be discontinued, and treatment should be converted to the SOC per major guidelines (ACCP 2012 guideline). Perioperative use of cardiopulmonary bypass (CPB) is not an exclusion; however, apixaban treatment should be interrupted during CPB as described in section 3.4.2, and intermittent anti-coagulation (e.g., UFH) should be used per current guideline recommendations (ACCP 2012 guideline).

In the event a female subject becomes pregnant during the clinical trial, the study drug must be discontinued immediately. In the case of pregnancy, the investigator must immediately notify the BMS Medical Monitor/designee of this event. Please call the BMS Medical Monitor within 24 hours of awareness of the pregnancy. If the investigator determines a possible favorable benefit/risk ratio that warrants continuation of study drug, a discussion between the investigator and the BMS Medical Monitor/designee must occur and a decision will be made on a case-by-case basis.

All subjects who discontinue study drug should comply with protocol specified follow-up procedures as outlined in [Section 5](#). The only exception to this requirement is when a subject withdraws consent for all study procedures including post-treatment study follow-up or loses the

ability to consent freely (i.e. is imprisoned or involuntarily incarcerated for the treatment of either a psychiatric or physical illness).

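### Read as written, the last-dose-plus-two-days safety window in 8.4.3 also governs all-cause death, so later deaths, unless counted as thromboembolic, have no stated by-arm summary despite two months of required follow-up

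*Combined protocol and SAP*

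**What the plan says.** Section 8.4.3 defines the treatment period as "the period between the first administration of study drug and two days after the last administration of study drug" and then states: "This period will be the basis for the summaries of safety". It names no exception. The secondary analyses that follow cover bleeding, adverse events and laboratory values, and add: "All AEs that are serious or that result in discontinuation of study drug will be described in depth". Death has no sentence of its own.

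Section 8.3.2 lists "All cause death" among the secondary safety endpoints. Section 8.2 sets who is counted: "The safety population for safety endpoints includes all subjects who receive at least one dose of study medication".

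One cause of death has a second route. The secondary efficacy endpoint takes in thromboembolic events "detected by imaging or clinical diagnosis, and thromboembolic event-related death". For that endpoint 8.4.2 says "Efficacy analyses will be based on intention to treat (ITT) population", but gives no end date.

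On conduct, 3.5 covers subjects who become ineligible during the study, for example one who "receives a VAD, ECMO, or a heart transplantation), study drug must be discontinued". Section 3.6 requires follow-up at Month 14, or two months after anticoagulation ends if that is sooner. It describes this follow-up as critical and asks for efficacy and safety outcomes and/or survival data as required. Table 5.1-2 schedules a serious adverse event assessment at that contact.

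**The concern.** A short on-treatment window suits bleeding. Section 3.3.1 equates five half-lives of apixaban with two days, so bleeding after that is hard to attribute to the drug. Death is different, because stopping the drug can itself result from deterioration. A child whose study drug is stopped for ECMO and who dies on day 5 after the last dose falls outside the window, although the event is recent and the protocol is still following the child.

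The primary objective (1.3.1) is to assess the safety of apixaban against VKA or LMWH. A death summary that stops two days after the last dose would leave unused most of the follow-up that 3.6 calls for. It would also be least informative for subjects treated briefly.

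**Working it through.** The plan gives no death rate, expected death count or precision figure that depends on this window, so there is no figure to reproduce. The check has two parts.

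**1. Does any passage give death another window?** Section 8.4.3 sets a general rule without exception, and 8.3.2 places all-cause death under safety. The protocol refers peri-procedural events (8.3.1, 8.3.2), subgroups (8.2) and the QOL method (8.4.6) to the SAP. It does not refer the safety window or the death analysis there. The synopsis places methods for secondary endpoints in the protocol. No passage gives all-cause death a different window.

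**2. How much follow-up is excluded?**

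Inputs:
- month = 30 days from randomisation (3.1)
- window ends at last dose + 2 days (8.4.3)
- follow-up contact at Month 14 ± 2 weeks, or 2 months ± 2 weeks after an early stop (3.1, 3.6)
- study drug ends at the Month 12 visit, itself ± 2 weeks (Table 5.1-2)
- minimum expected need for anticoagulation: 1 month under age 2, 6 months from age 2 (3.1)
- simplification: first dose on the day of randomisation

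Excluded days = contact day − (last-dose day + 2).

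- Nominal: 60 − 2 = 58 of 60 days.
- Early stop, contact ± 2 weeks: 46 − 2 = 44 to 74 − 2 = 72 days.
- Completers, using both visit windows: the last dose falls on day 346 to 374 and the contact on day 406 to 434. The range is 406 − 376 = 30 to 434 − 348 = 86 days.

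Share of time from first dose to final contact = excluded days / contact day:

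| Treatment | Nominal | Range |
|---|---|---|
| 12 months | 58/420 = 13.8% | 30/406 = 7.4% to 86/434 = 19.8% |
| 6 months | 58/240 = 24.2% | 44/226 = 19.5% to 72/254 = 28.3% |
| 1 month | 58/90 = 64.4% | 44/76 = 57.9% to 72/104 = 69.2% |

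The 1-month row is the extreme case: it is the minimum expected need under age 2, not a typical duration.

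**Collection.** Section 6.1.1 requires all serious adverse events, related or not, only for 30 days after dosing ends. Of those days, 30 − 2 = 28 already lie outside the analysis window. From day 31 to about day 60, 6.1.1 obliges the investigator to report only events believed related to study drug or a protocol procedure. Section 3.6 and Table 5.1-2 nevertheless look to the two-month contact for safety and survival information.

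**The case against.** The strongest reply is that 8.4.3 specifies no death table, so the omission is inferred from one general sentence. The words limiting secondary analyses to the end of the treatment period are attached only to bleeding. That is fair as far as it goes: the plan nowhere says that late deaths will be dropped. But the general sentence is a stated rule, and an analyst who follows it for a listed safety endpoint gets this result. If the rule was not meant for death, the endpoint has no stated analysis. The same added sentence answers both.

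Second, an SAP could settle the point. No separate SAP text was available, so this cannot be excluded. An SAP that used a longer window for death would, however, depart from 8.4.3 rather than fill a gap left open for it.

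Third, late deaths are not invisible. Thromboembolic deaths may be counted under ITT, deaths are adjudicated blind, serious events are described individually, and the DSMB reviews outcomes. All of this stands. What remains uncovered is a by-arm summary of late non-thromboembolic deaths, which case descriptions do not replace.

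Fourth, an on-treatment window in dosed subjects is a coherent convention, and after the last dose subjects move to standard of care. This is a real cost of a longer window and a reason to keep the on-treatment count beside it.

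A reader might go further in four ways that the documents do not support:

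- **That the comparison of death rates is biased.** This would need stopping for deterioration to differ by arm, and nothing in the documents shows that it will.
- **That the time shares are shares of deaths.** With no death rate given, before or after stopping, any conversion rests on an invented rate.
- **That up to 86 days are lost after an early stop.** The early-discontinuation paragraph in 3.1 can be read as counting two months from an evaluation two weeks after the stop. The definition of the last visit in the same section counts from discontinuation, and 3.6 agrees with it.
- **That waiting for the INR to fall before the first apixaban dose creates an important gap at the start.** Table 5.5-1, note a, allows for such a wait, but its length and frequency are not given. Section 3.1 expects the first dose at the centre following randomisation.

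**Conclusion.** The point holds as a reading of the text. The general safety window in 8.4.3 applies to all-cause death because nothing exempts it, and it excludes nominally 58 of 60 follow-up days. The excluded range is about 30 to 86 days for completers and 44 to 72 days after an early stop. The nominal share of observed time runs from 13.8% at 12 months of treatment to 64.4% at 1 month.

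This rests on three things: that any by-arm death summary would follow the general rule, that no SAP says otherwise, and that the first dose is given at randomisation. The number of deaths affected is unknown and no bias between arms has been shown. This is a secondary endpoint in a descriptive study, but comparative safety is the study's purpose and the gap is easy to avoid, so it should be corrected. The bleeding window is not in question.

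**What to change.** 1. In 8.4.3, summarise all-cause death by arm in all randomised subjects, from randomisation to the final follow-up contact (Month 14, or two months after stopping). Show deaths up to last dose + 2 days in dosed subjects as a subset.
2. In 8.2, note this as an exception to the dosed-only safety population.
3. In 6.1.1, state that every death, related or not, is recorded through the final contact.
4. Two minor clarifications: give the end date for thromboembolic event-related death in 8.4.2, and reconcile the early-stop timing within 3.1.

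The cost is a few sentences and a few tables. No visit is added, since the contact is already scheduled. Item 3 does make explicit a recording duty that 6.1.1 now limits to 30 days for unrelated events. The drawback is that the longer window includes time on standard of care, which is why the on-treatment subset is kept. No sample size or power figure changes.

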8.4.4 Pharmacokinetic Analyses

Samples collected for pharmacokinetic analysis will be analyzed by LC-MSMS to determine apixaban plasma concentration. A PPK model will be developed using plasma concentration versus time data. Model-derived population and individual PK parameters (e.g., CL/F, Vc/F, KA) will be used to estimate Cmax, Cmin, and AUC(TAU) in each subject. Details of the analyses will be described in a separate population PK/PD modeling analysis plan document and results will be presented in a separate population PK/PD report. Summary Statistics will be provided by age- and weight-group as appropriate. Listings of individual observed PK will be provided by visit, weight- and age-group as appropriate.

8.4.6 Outcomes Research Analyses

The analysis method for QOL will be provided in the statistical analysis plan. It is anticipated that apixaban may have more impact on KIDCLOT© that measures the treatment effect of an anticoagulant, and may have less impact on PedsQL generic core and cardiac modules that measures disease burden.

8.4.7 Other Analyses

Not applicable.

8.5 Interim Analyses

There will be no formal interim efficacy analysis because this is not a Phase 3 trial powered for efficacy.

Interim safety analysis will be performed per the DSMB requirement. The DSMB will review safety and efficacy outcomes as defined in the DSMB charter. Detailed monitoring rules will be provided in the DSMB data monitoring plan. The DSMB may recommend termination of the study or any of the study arms for an important safety concern that is felt to outweigh potential benefits.

9 STUDY MANAGEMENT

9.1 Compliance

9.1.1 Compliance with the Protocol and Protocol Revisions

The study shall be conducted as described in this approved protocol. All revisions to the protocol must be discussed with, and be prepared by, BMS. The investigator should not implement any deviation or change to the protocol without prior review and documented approval/favorable opinion from the IRB/IEC of an amendment, except where necessary to eliminate an immediate hazard(s) to study subjects.

If a deviation or change to a protocol is implemented to eliminate an immediate hazard(s) prior to obtaining IRB/IEC approval/favorable opinion, as soon as possible the deviation or change will be submitted to:

- IRB/IEC for review and approval/favorable opinion
- BMS
- Regulatory Authority(ies), if required by local regulations

Documentation of approval signed by the chairperson or designee of the IRB(s)/IEC(s) must be sent to BMS.

If an amendment substantially alters the study design or increases the potential risk to the subject: (1) the consent form must be revised and submitted to the IRB(s)/IEC(s) for review and approval/favorable opinion; (2) the revised form must be used to obtain consent from subjects currently enrolled in the study if they are affected by the amendment; and (3) the new form must be used to obtain consent from new subjects prior to enrollment.

If the revision is done via an administrative letter, investigators must inform their IRB(s)/IEC(s).

9.1.2 Monitoring

BMS representatives will review data centrally to identify potential issues to determine a schedule of on-site visits for targeted review of study records.

Representatives of BMS must be allowed to visit all study site locations periodically to assess the data quality and study integrity. On site they will review study records and directly compare them with source documents, discuss the conduct of the study with the investigator, and verify that the facilities remain acceptable. Certain CRF pages and/or electronic files may serve as the source document:

In addition, the study may be evaluated by BMS internal auditors and government inspectors who must be allowed access to CRFs, source documents, other study files, and study facilities. BMS audit reports will be kept confidential.

The investigator must notify BMS promptly of any inspections scheduled by regulatory authorities, and promptly forward copies of inspection reports to BMS.

9.1.2.1 Source Documentation

The Investigator is responsible for ensuring that the source data are accurate, legible, contemporaneous, original and attributable, whether the data are hand-written on paper or entered electronically. If source data are created (first entered), modified, maintained, archived, retrieved, or transmitted electronically via computerized systems (and/or any other kind of electronic devices) as part of regulated clinical trial activities, such systems must be compliant with all applicable laws and regulations governing use of electronic records and/or electronic signatures. Such systems may include, but are not limited to, electronic medical/health records (EMRs/EHRs), adverse event tracking/reporting, protocol required assessments, and/or drug accountability records).

When paper records from such systems are used in place of electronic format to perform regulated activities, such paper records should be certified copies. A certified copy consists of a copy of original information that has been verified, as indicated by a dated signature, as an exact copy having all of the same attributes and information as the original.

9.1.3 Investigational Site Training

BMS will provide quality investigational staff training prior to study initiation. Training topics will include but are not limited to: GCP, AE reporting, study details and procedure, electronic CRFs, study documentation, informed consent, and enrollment of WOCBP.

9.2 Records

9.2.1 Records Retention

The investigator must retain all study records and source documents for the maximum period required by applicable regulations and guidelines, or institution procedures, or for the period specified by BMS, whichever is longer. The investigator must contact BMS prior to destroying any records associated with the study.

BMS will notify the investigator when the study records are no longer needed.

If the investigator withdraws from the study (e.g., relocation, retirement), the records shall be transferred to a mutually agreed upon designee (e.g., another investigator, IRB). Notice of such transfer will be given in writing to BMS.

9.2.2 Study Drug Records

Records for IP (whether supplied by BMS, its vendors, or the site) must substantiate IP integrity and traceability from receipt, preparation, administration, and through destruction or return. Records must be made available for review at the request of BMS/designee or a Health Authority.

| If... | Then... |
|--|---|
| Supplied by BMS (or its vendors): | 
 • Records or logs must comply with applicable regulations and guidelines and should include: • amount received and placed in storage area • amount currently in storage area • label identification number or batch number • amount dispensed to and returned by each subject, including unique subject identifiers • amount transferred to another area/site for dispensing or storage • nonstudy disposition (e.g., lost, wasted) • amount destroyed at study site, if applicable • amount returned to BMS • retain samples for bioavailability/bioequivalence, if applicable • dates and initials of person responsible for Investigational Product dispensing/accountability, as per the Delegation of Authority Form |
| Sourced by site, and not supplied by BMS or its vendors (examples include IP sourced from the sites stock or commercial supply, or a specialty pharmacy) | 
The investigator or designee accepts responsibility for documenting traceability and study drug integrity in accordance with requirements applicable under law and the SOPs/standards of the sourcing pharmacy. These records should include:
 
 • label identification number or batch number • amount dispensed to and returned by each subject, including unique subject identifiers • dates and initials of person responsible for Investigational Product dispensing/accountability, as per the Delegation of Authority Form. |

BMS or designee will provide forms to facilitate inventory control if the investigational site does not have an established system that meets these requirements.

